2 LIST OF ABBREVIATIONS

Abbreviation	Term
AE	adverse event
ALP	alkaline aminotransferase
ALT	alanine aminotransferase
ANCOVA	analysis of covariance
AR(1)	autoregressive model of order 1
AST	aspartate aminotransferase
AT	Anaerobic threshold
BMI	body mass index (kg/m ²)
bpm	beats per minute
CF	cystic fibrosis
CFQ-R	Cystic Fibrosis Questionnaire – Revised
CFTR	cystic fibrosis transmembrane conductance regulator
CI	confidence interval
CMH	Cochran-Mantel-Haenszel
CPET	Cardiopulmonary exercise testing
CRF	case report form
CRO	contract research organization
DMC	data monitoring committee
ECG	electrocardiogram
eCRF	electronic case report form
FAS	full analysis set
FEF _{25-75%}	forced expiratory flow, midexpiratory phase
FEV ₁	forced expiratory volume in 1 second
FVC	forced vital capacity
F508del	CFTR gene mutation with an in-frame deletion of a phenylalanine codon corresponding to position 508 of the wild-type protein
GAD-7	Generalized Anxiety Disorder
HNV _{FEV}	Hankinson predicted value of FEV ₁ (L)
HNV _{FEF25-75%}	Hankinson predicted value of FEF _{25-75%} (L/sec)
HNV _{FVC}	Hankinson predicted value of FVC (L)
ISE	integrated summary of efficacy
LFT	liver function test
LOCF	last observation carried forward
M1	VRT-837018, hydroxymethyl-ivacaftor, metabolite of ivacaftor
M6	VRT-842917, carboxy-ivacaftor, ivacaftor acid, metabolite of ivacaftor
MH	Mantel-Haenszel
max	maximum value
MedDRA	Medical Dictionary for Regulatory Activities
MI	multiple imputation
min	minimum value
MMRM	mixed model repeated measure
N	number of subjects

Abbreviation	Term
PD	pharmacodynamic/pharmacodynamics
PHQ-8	Patient Health Questionnaire
PK	pharmacokinetic/pharmacokinetics
PPS	per protocol set
PT	preferred term
q12h	every 12 hours
QRS	Q, R, and S-wave define the QRS-complex in an ECG
QT	QT interval: The duration of ventricular depolarization and subsequent repolarization; it is measured from the beginning of the QRS complex to the end of the T wave
QTc	QT interval corrected for heart rate
QTcF	QT interval corrected for heart rate with Fridericia's correction
SAE	serious adverse event
SAP	Statistical Analysis Plan
SD	standard deviation
SE	standard error
SI	System International
SOC	system organ class
TEAE	treatment-emergent adverse event
TSQM	Treatment Satisfaction Questionnaire for Medication
ULN	upper limit of normal
VCO ₂	Carbon dioxide production
VO ₂	Oxygen consumption
VO ₂ max	Maximal Oxygen consumption
WNV _{FEV}	Wang predicted value of FEV ₁ (L)
WNV _{FEF25-75%}	Wang predicted value of FEF _{25-75%} (L/sec)
WNV _{FVC}	Wang predicted value of FVC (L)
WHODDE	World Health Organization Drug Dictionary Enhanced

3 SUMMARY OF MODIFICATIONS

No applicable as of 01 August 2016

4 INTRODUCTION

This SAP describes the planned final analyses for the Study VX15-809-112 data and is based on the

- approved clinical study protocol (Version 1.0, dated 15 January 2016),
- approved electronic case report form (eCRF) (dated 13 January 2017).

Study VX15-809-112 is a Phase 4, Randomized, Double-Blind, Placebo-Controlled, Parallel-Design Study of the Effect of Lumacaftor/Ivacaftor Combination Therapy on Exercise Tolerance in Subjects Aged 12 Years and Older With Cystic Fibrosis, Homozygous for the *F508del-CFTR* Mutation.

This SAP (Methods) documents the planned final statistical analyses of efficacy and safety introduced in the study protocol of VX15-809-112, and describes the corresponding data presentations. It also documents additional efficacy and safety analyses not specified in the protocol, which will provide supportive information to the scientific understanding of the drug entity.

The [REDACTED] Biostatistics Department will perform the statistical analysis of the efficacy and safety data under the supervision of Vertex Biometrics Department; SAS (Version 9.2, or higher) will be used to generate all statistical outputs (tables, figures, listings, and datasets). The SAP will be finalized and approved prior to the final clinical data lock and treatment unblinding for the study.

5 STUDY OBJECTIVES

5.1 Primary Objective

To evaluate the effect of LUM/IVA on exercise tolerance in subjects with CF, homozygous for the *F508del-CFTR* mutation

5.2 Secondary Objectives

To evaluate the effect of LUM/IVA on manifestations of CF affected by exercise tolerance and training

6 STUDY ENDPOINTS

6.1 Efficacy Endpoints

6.1.1 Primary Endpoint

Relative change from baseline in VO_2 max during cardiopulmonary exercise testing (CPET) at Week 24

6.1.2 Secondary Endpoints

Key Secondary Endpoint

- Relative change from baseline in exercise duration during CPET at Week 24

Other Secondary Endpoints

- Absolute change from baseline in exercise duration during CPET at Week 24
- Absolute change from baseline in VO_2 max during cardiopulmonary exercise testing (CPET) at Week 24
- Absolute and relative change from baseline in oxygen consumption (VO_2) at anaerobic threshold (AT) (the point during exercise at which lactate starts to accumulate) at Week 24
- Absolute and relative change from baseline in functional VO_2 gain at Week 24
- Absolute and relative change from baseline in the slope of pulmonary ventilation (VE) versus carbon dioxide production (VCO_2) at Week 24
- Absolute change from baseline in percent predicted forced expiratory volume in 1 second (ppFEV₁) at Week 24
- Relative change from baseline in percent predicted forced expiratory volume in 1 second (ppFEV₁) at Week 24
- Absolute change from baseline in body mass index (BMI) at Week 24
- Relative change from baseline in body mass index (BMI) at week 24
- Absolute change from baseline in Cystic Fibrosis Questionnaire-Revised (CFQ-R) respiratory domain score at Week 24
- Absolute change from baseline in overall Patient Health Questionnaire (PHQ-8) and Generalized Anxiety Disorder (GAD-7) scores at Week 24
- Absolute change from baseline in total daily physical activity as determined by actigraphy at Week 24
- Relative change from baseline in total daily physical activity as determined by actigraphy at Week 24
- Absolute change from baseline in duration of sleep time during the night at Week 24

- Relative change from baseline in duration of sleep time during the night at Week 24
- Absolute change from baseline in time above sedentary duration at Week 24
- Relative change from baseline in time above sedentary duration at Week 24

6.2 Safety Endpoints

The safety endpoints are as follows:

- Adverse events
- Clinical laboratory
- Vital signs
- Pulse oximetry
- Physical examination
- Ophthalmologic findings (for subjects under 18 years of age only)

6.3 Pharmacokinetic Endpoints

Not applicable

7 STUDY DESIGN

[figure not shown]
7.1 Overall Design

This is a Phase 4, randomized, double-blind, placebo-controlled, parallel-group study in subjects aged 12 years and older with CF who are homozygous for the *F508del-CFTR* mutation. This study is designed to evaluate the effect of LUM/IVA on exercise tolerance.

The study includes a Screening Period, a Treatment Period, and a Safety Follow-up Visit. Approximately 66 subjects will be randomized 1:1 (LUM/IVA: placebo) to the treatment arms shown in Figure 7-1 and stratified by ppFEV₁ at baseline (<70% and ≥70% predicted). Subjects will receive study drug (LUM/IVA or placebo) for 24 weeks, in addition to their current CF medication regimen. They will return to the study center 4 weeks after their last dose of study drug for the Safety Follow-up Visit. It is recommended that subjects remain on

a stable CF medication regimen from 4 weeks before Day 1 through the Safety Follow-up Visit.

[figure not shown]
Subjects will be reminded of the standard exercise recommendations for patients with CF, and their daily activity will be tracked using an actigraphy device.

About Cardiopulmonary exercise testing (CPET)

CPET will be performed at the time points noted in study schedule. CPET will be conducted using the Godfrey protocol¹, which has been used in a number of studies of exercise tolerance in patients with CF. According to the Godfrey protocol, CPET will be conducted using a cycle that ramps resistance over time. Pulse oximetry is utilized during CPET.

Figure 7-1 Schematic View of the Study Design

7.2 Sample Size and Power

Assuming a common standard deviation (SD) of 10% for the primary efficacy endpoint and a dropout rate of 10%, a sample size of 33 subjects in each treatment group would provide at least 80% power to detect a difference of 7.5% between the means for the 2 treatment groups using a 2-sided test at the 0.05 significance level. If the true difference is smaller, or if there

is greater variability, a larger sample size would be required to provide 80% power. Table 7-1 shows the required sample sizes for various assumptions about the true treatment effect using a 2-sided test at the 0.05 significance level.

Because LUM/IVA has recently been approved in several countries, additional data independent of this study may emerge while this study is underway, which would allow a more precise estimation of the true treatment effect. The final sample size may be recalculated based on these data, and the protocol may be amended as appropriate.

Table 7-1 Sample Sizes for 80% Power

True Difference Between Placebo and LUM/IVA Effects on Primary Endpoint	Sample Size Needed for 80% Power (subjects per treatment group)
5.0%	72
5.5%	59
6.0%	50
6.5%	44
7.0%	38
7.5%	33

7.3 Randomization

A total of approximately 66 subjects (33 per arm) who meet eligibility criteria will be stratified by age (<18 versus \geq 18 years of age), sex (male versus female), and percent predicted FEV₁ severity determined at the baseline Visit (<70 versus \geq 70), and then randomized (1:1) to 1 of the 2 treatment arms.

The randomization codes were produced by a designated vendor [REDACTED]. In order to protect the study blind and maintain the scientific integrity of the data, 1 Vertex biostatistician and 1 [REDACTED] biostatistician were involved in the randomization process for each study: a Vertex biostatistician who is blinded to the actual treatment code and a [REDACTED] unblinded biostatistician who is not associated with the study. Below is a brief description of the randomization process.

- The Vertex biostatistician created the randomization specification.
- The external designated vendor [REDACTED] created the dummy randomization code, which was reviewed and approved by the Vertex biostatistician.
- After approval, the external designated vendor generated the production randomization list and provided it to the unblinded [REDACTED] biostatistician for review.
- After all outstanding issues were resolved; the external designated vendor generated the final randomization list and provided it to the unblinded [REDACTED] biostatistician to upload in the designated final randomization study area.

The unblinded [REDACTED] biostatistician provided the final randomization list to the interactive web response system (IWRS) vendor. A copy of the final randomization list, provided in sealed tamper-evident envelopes, was archived at Vertex.

7.4 Blinding and Unblinding

7.4.1 Blinding

All subjects, site personnel including the investigator, the site monitor, and the Vertex study team will be blinded for the duration of the study, with the exception of the following:

- Any site personnel for whom this information is important to ensure the safety of the subject in the event of a life-threatening medical emergency
- Any site personnel for whom this information is important to ensure the safety of the subject and their fetus in the event of a pregnancy
- Vertex Global Patient Safety (GPS) and Regulatory Affairs personnel to satisfy serious adverse event (SAE) processing and reporting regulations
- Unblinded statistician preparing the final (production) randomization list who is not part of the study team
- Vertex Clinical Operations IWRS management
- Vertex Clinical Supply Chain
- DMC
- Vertex medical monitor may, for matters relating to safety concerns, unblind individual subjects at any time

Subjects and their caregiver should not be informed of their study-related spirometry results during the Treatment Period regardless of whether the subject has prematurely discontinued treatment.

Vertex Drug Metabolism and Pharmacokinetics laboratory personnel will not be involved in the conduct of the study and will be unblinded to the bioanalysis results but will remain blinded to subject number and treatment assignment.

7.4.2 Unblinding

Unblinding of the individual subject's treatment by the investigator should be limited to medical emergencies or urgent clinical situations in which knowledge of the subject's study treatment is necessary for clinical management. Details are provided in the clinical study protocol Section 11.12.2.

If a subject's treatment assignment has been unblinded for a medical emergency or urgent clinical situation, the Vertex medical monitor should be notified within 24 hours of the unblinding event. The reason and the date of the unblinding should be documented clearly in the subject's source documents. Information regarding the treatment assignment obtained

from the unblinding should be maintained in a secure location with controlled access and must not be shared with Vertex, contract research organizations (CROs), or any site personnel (other than the physician treating the subject). In addition, the investigator should consider whether the clinical event that prompted unblinding should be considered an SAE, according to the regulatory definitions or criteria for SAEs, and if so, submit an SAE report to Vertex GPS, per corresponding section of the clinical study protocol.

Vertex GPS or designee will also unblind any SAE reports in compliance with regulatory reporting requirements. In addition, the Vertex medical monitor may, for matters relating to safety concerns, unblind individual subjects at any time.

8 ANALYSIS SETS

Assignment of subjects to analysis sets will be done prior to clinical data lock for the study.

The following analysis sets will be defined: All Subjects Set, Full Analysis Set (FAS) and Safety Set.

The All Subjects Set will be defined as all subjects in the study who were randomized or dosed (received any amount of study drug). All subject data listings will be use the All Subjects Set, unless otherwise specified.

8.1 Efficacy Sets

8.1.1 Full Analysis Set (FAS)

The FAS will include all randomized subjects who received any amount of study drug. The treatment assignment for the FAS will be as randomized. The FAS will be used for all efficacy analyses.

8.2 Safety Set

The Safety Set will include all subjects who received any amount of study drug. The treatment assignment for the Safety Set will be as treated. All safety analyses will be conducted using the Safety Set.

8.3 Other Analysis Set

Not applicable.

9 STATISTICAL ANALYSIS

9.1 General Considerations

The Schedule of Assessments is provided in Appendix A.

All individual subject data for those randomized or exposed to study drug will be presented in data listings.

Continuous variables will be summarized using the following descriptive summary statistics: the number of subjects (n), mean, standard error (SE), standard deviation (SD), median, minimum value (min), and maximum value (max). The precision of the measurement for each continuous variable will be used to determine the number of decimal places to present in tables, figures, and derived listings. Minimum and maximum values will be reported with the same precision as the units of measure. The mean and median will be reported to 1 greater decimal place, and the SE and SD will be reported to 2 additional decimal places. Any values that require transformation to standard units (metric or SI) will be converted with the appropriate corresponding precision.

Categorical variables will be summarized using counts and percentages. Percentages will be presented to 1 decimal place.

Baseline Value: Unless otherwise specified, the baseline value will be defined as the most recent non-missing measurement (scheduled or unscheduled) collected prior to the initial administration of study drug. Baseline CPET data will be collected on Day 1 prior to the initial administration of study drug. Unscheduled visit measurements will be included for derivation of baseline. For actigraphy variables, baseline data will be defined as the mean of the data collected for the 7 days immediately preceding Day 1 (Day -7 to Day -1) during the Screening Period.

Absolute Change from baseline will be calculated as Post baseline value - Baseline value.

Relative change from baseline will be calculated and expressed in percentages as $100 \times \frac{(\text{Post baseline value} - \text{Baseline value})}{\text{Baseline value}}$.

Unscheduled Visits: Unscheduled visit measurements will be included in listings, for derivation of visit windows and computation of baseline/last on-treatment visit, and for the analysis of maximum/minimum on-treatment values and maximum/minimum changes from baseline values.

Visit Windows: Appendix C defines the visit window mapping rules to derive the analysis visits.

Repeated observations within the same visits window

- For all efficacy parameters, if there are multiple measurements within a visit window, the record at the scheduled visit will be used. If there are no measurements at the scheduled visit, then 1) the record closest to the target day will be used; or 2) if there are multiple records with the same distance to the target day, the latest record will be used.
- For all safety parameters, if there are multiple measurements within a visit window, then 1) the record closest to the target day will be used; or 2) if there are multiple records with the same distance to the target day, the latest record will be used.

BMI will follow visit window rules for efficacy parameters when being considered as an efficacy endpoint.

Incomplete/Missing data will not be imputed, unless otherwise specified; i.e., all missing values will remain as missing in all statistical analyses and listings, unless otherwise specified. Missing post-baseline values will not be imputed for efficacy analysis conducted

using a mixed model for repeated measures (MMRM) approach, which makes use of all available data even if a subject has missing data at some post-baseline visits.

Outliers: No formal statistical analyses will be performed to detect and/or remedy the presence of statistical outliers.

Repeated Observations: Measurements recorded at different time points are defined as repeated observations. If an assessment has planned repeated measurements, then statistical summaries will present all planned time points, as appropriate.

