9.3 Efficacy Analysis

Unless otherwise defined, all efficacy analyses described in this section will include all measurements up to Week 24 [inclusive], both on-treatment measurements and measurements after treatment discontinuation.

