9.3.1.2 Primary Analysis of Primary Efficacy Endpoint

The primary analysis for the primary efficacy endpoint will be based on a mixed model repeated measures (MMRM) using SAS PROC MIXED based on the FAS.

The model, including percentage change from baseline in $VO_2\text{max}$ (including all measurements up to Week 24 [inclusive], both on-treatment measurements and measurements after treatment discontinuation) as the dependent variable, treatment, visit, and treatment-by-visit interaction as fixed effects, with adjustment for sex (male versus female), age group at baseline (<18 versus \geq 18 years old), percent predicted FEV₁ at baseline (<70

versus ≥ 70), baseline $VO_2\text{max}$ value and subject as a random effect will be used to test the difference between active treatment group versus placebo. The primary result obtained from the model will be the treatment effect at Week 24.

Descriptive summary statistics including number of subjects, mean, standard error, and least-square means (LS means) along with the P values will be provided. In particular, the difference in LS means as well as LS means within each group and the corresponding 95% CI will be provided along with the P values to assess the treatment difference between placebo and lumacaftor in combination with ivacaftor. Additionally, the P value testing the treatment-by-visit interaction will be provided to assess the consistency of treatment effect over different visits.

The repeated-measures analysis will be based on the restricted maximum likelihood method assuming an unstructured covariance structure to model the within-subject errors. A Kenward-Roger approximation will be used for the denominator degrees of freedom. If there is a convergence problem due to the unstructured covariance matrix, a compound symmetry covariance structure will be used to model the within-subject errors. With a mixed effects model as the primary analysis model based on restricted maximum likelihood estimation and assuming that conditional on fixed and random effects, data are missing at random, no imputation of missing data will be done.

In addition, raw values of percentage change from baseline in $VO_2\text{max}$ at Week 24, and raw values of percentage change from baseline in $VO_2\text{max}$ at Week 12 will be summarized descriptively (number, mean, SE, SD, median, min, and max).

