Appendix G Important Protocol Deviation Programming Rules (Based on the Clinical Database)

Important protocol deviations before first dose

1. Individual screening assessment(s) that did not meet eligibility criteria, excluding the exceptions that are permitted per protocol, were repeated
2. Screening visit performed outside of the -28 to -1 day window
3. Subject randomized and screening ophthalmologic examination greater than 3 months prior to Screening Visit
4. Height not collected for subjects who were 21 years of age or younger at the Screening Visit.

Important protocol deviations during treatment period

5. ETT visit was less than 3 weeks after the last dose of study drug but no Safety Follow-up Visit was performed.
6. After subject study completion/early discontinuation, prior study visits not done
7. Subject who prematurely discontinues study drug treatment did not complete the ETT visit
8. CPET not performed per protocol schedule
9. Prohibited medication taken during study
10. Initial dose of study drug not administered on Day 1.

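### A Week 12 exercise test done more than 7 days late is mapped to Week 24, and if no later test falls in that window it becomes the subject's primary value

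*SAP*

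**What the plan says.** SAP 9.1 takes the analysis visit from the calendar: "Appendix C defines the visit window mapping rules to derive the analysis visits". For CPET, Table 12-3 in Appendix C gives:

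| Analysis visit | Target day | Study days mapped to it |
|---|---|---|
| Week 12 | 85 | 2 to 92 |
| Week 24 | 169 | 93 to 176 |
| Safety follow-up | 197 | 177 to 204 |

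The same windows serve spirometry, the questionnaires and weight. Protocol Table 3-2 allows ±7 days around Week 12 and around Week 24.

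When one window holds several efficacy records, SAP 9.1 says: "For all efficacy parameters, if there are multiple measurements within a visit window, the record at the scheduled visit will be used". The fallback reads: "If there are no measurements at the scheduled visit, then 1) the record closest to the target day will be used". On missing data, 9.1 says: "Missing post-baseline values will not be imputed for efficacy analysis conducted" by MMRM. SAP 9.3 brings in all measurements up to Week 24, "both on-treatment measurements and measurements after treatment discontinuation". SAP 9.3.1.2 states: "The primary result obtained from the model will be the treatment effect at Week 24".

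Appendix G lists "CPET not performed per protocol schedule" among the important protocol deviations. Neither document removes such a test from the Full Analysis Set analysis, and neither says that a test done at the nominal Week 12 visit keeps its Week 12 label.

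**The concern.** The boundary between the two windows is the end of the protocol's Week 12 allowance. A Week 12 visit that overruns the allowance by a single day therefore changes label, although it is still far nearer Week 12 than Week 24. Two things can follow.

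- The subject also has a Week 24 test in the window. Two records from scheduled visits then share it, and the text does not say which scheduled visit is meant.
- The subject has no later test in the window. A measurement taken after about 13 weeks then stands as the 24-week outcome.

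The second matters more, because Week 24 is the primary contrast. The SAP leaves a missing Week 24 value missing and relies on the MMRM. Relabelling instead enters a Week 12 result at Week 24 and counts the subject as observed there.

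**Working it through.** **1. Day arithmetic.** Targets: 12 × 7 + 1 = 85 and 24 × 7 + 1 = 169, as in Table 12-3. With ±7 days the protocol permits Days 78 to 92 for Week 12 and Days 162 to 176 for Week 24.

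**2. The boundary.**

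| Study day | Days from 85 | Days from 169 | Mapped to |
|---|---|---|---|
| 86 | 1 | 83 | Week 12 |
| 92 | 7 | 77 | Week 12 |
| 93 | 8 | 76 | Week 24 |
| 126 | 41 | 43 | Week 24 |
| 127 | 42 | 42 | Week 24 |
| 128 | 43 | 41 | Week 24 |

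The midpoint of the targets is (85 + 169)/2 = 127. The Week 24 window has 176 − 93 + 1 = 84 days. Of these, 126 − 93 + 1 = 34 are nearer the Week 12 target, and 161 − 93 + 1 = 69 precede the earliest protocol day for Week 24.

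**3. A nominal Week 12 CPET on Day 93, traced through the rules.**

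| Later CPET | Week 12 value | Week 24 value |
|---|---|---|
| Week 24 visit by Day 176 | Empty | True Week 24 test, on the natural reading of 9.1 |
| None | Empty | The Day 93 test, from Table 12-3 alone |
| Week 24 visit on Day 177 or later | Empty | The Day 93 test; the later one maps to safety follow-up |
| Early-termination visit, Days 94 to 176 | Empty | Early-termination test if only a Week 24 visit counts as the scheduled one; otherwise the Day 93 test |

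The multiple-record rule acts only in the first and last rows. In the middle two, the window holds one record and the mapping decides.

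**4. The plan's own figure.** SAP 7.2 assumes SD 10%, difference 7.5%, two-sided 0.05, 80% power and 10% dropout. A two-sample t-test (noncentral t) needs 29 evaluable per arm (power 80.1%), and 29/0.90 = 32.2, rounded up to 33. The same method reproduces all six rows of Table 7-1, so the sample size is not in question. Below I use 33 × 0.9 = 29.7, rounded to 30 evaluable per arm, for which power is 81.5%.

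**5. Size.** The documents give neither the number of late tests nor the Week 12 effect, so both are assumed. Let r be the Week 12 effect as a fraction of the Week 24 effect, with the placebo change taken as equal at the two visits. One relabelled active subject lowers the active Week 24 mean by (1 − r) × 7.5/30:

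| r | Shift (points) |
|---|---|
| 0.8 | 0.05 |
| 0.5 | 0.125 |
| 0 | 0.25 |

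The standard error of the difference is 10 × √(2/30) = 2.58, so each such subject costs 0.05/2.58 = 2% to 0.25/2.58 = 10% of one standard error.

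If a share f of Week 24 values is affected, the expected difference is 7.5 × [1 − f(1 − r)]:

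| f | r | Expected difference | Power, 30 per arm |
|---|---|---|---|
| 0 | any | 7.50 | 81.5% |
| 3% | 0.8 | 7.46 | 81.0% |
| 3% | 0.5 | 7.39 | 80.3% |
| 10% | 0.8 | 7.35 | 79.9% |
| 10% | 0.5 | 7.13 | 77.4% |

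These shifts compare a relabelled value with a true Week 24 value. When no Week 24 test exists, the proper comparison is with a Week 12 value plus a missing Week 24 value in the MMRM. That needs a within-subject correlation the documents do not give, and I have not calculated it.

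**The case against.** The sponsor could fairly say the following.

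- **Only deviations are touched.** Every Week 12 CPET done within protocol, Days 78 to 92, is labelled correctly. This stands. A reader might infer that any test a day past its target is misfiled; Day 86 is still Week 12.
- **The multiple-record rule protects the primary endpoint.** Inside the Week 24 window, the scheduled visit most naturally means the Week 24 visit. This also stands. A reader might infer that this rule turns the late test into the primary value, but it applies only when there are several records; for a lone record Table 12-3 does it. With both visits in the window, the cost is one missing Week 12 value.
- **Appendix G does not forecast late tests.** It is a list of programmed checks that includes events such as prohibited medication. Naming an off-schedule CPET there does not show that such tests are expected. This stands.
- **The discard does not strip the model of data on dropouts.** With no later test, the late one is kept under the wrong label; with a Week 24 test in the window, the subject is observed at the primary visit. What is lost there is a Week 12 value and a Week 12/Week 24 pair. This stands.
- **The windows follow a convention.** All three end 7 days after target, and a midpoint cut is only another convention. True, but the convention does not answer the labelling point: a test known to come from the Week 12 visit is still analysed as Week 24.

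The sponsor might add that nominal labels are implied by the reference to the scheduled visit. That phrase operates only after Table 12-3 has already placed the record in a window, so it cannot restore a Week 12 label.

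**Conclusion.** The point holds as a labelling defect confined to Week 12 tests done on Day 93 or later. With a Week 24 test by Day 176, the late test is discarded and the primary value is unaffected, on the natural reading of SAP 9.1. With no later CPET in the window, a roughly 13-week result becomes that subject's primary Week 24 value by the mapping alone.

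Primary contamination thus needs two events in one subject: a Week 12 CPET more than 7 days late, and no later CPET in the window. The documents give no frequency for either. Under the assumptions shown, the shift is 0.05 to 0.25 points per relabelled active subject, well below one standard error. A reader might infer that the primary result is materially biased. The documents do not support that; it would take several such subjects and a Week 12 effect well short of the Week 24 effect. The wrong label is certain whenever the conditions are met, and it is cheap to prevent.

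**What to change.** State in SAP 9.1 and Appendix C that a record from a nominal Week 12 or Week 24 visit keeps that visit's label, and that the day windows apply only to records without a nominal visit, that is unscheduled or early-termination records. This resolves every row of the trace above. It also means that a Week 24 CPET done after Day 176 counts as Week 24 rather than safety follow-up, which should be said openly.

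Moving the cut to the midpoint for the remaining records (Week 12 to Day 127, Week 24 from Day 128) is optional. Its downside is that early-termination CPETs on Days 93 to 127 would no longer count as Week 24 values, although SAP 9.3 deliberately includes measurements after discontinuation. The nominal-label sentence is enough without it.

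The cost is one sentence and a small programming change, made before data lock and unblinding. It needs no new data, no protocol amendment and no change in sample size.
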